8 ASSESSMENT OF SAFETY

8.1 Definitions of Safety Parameters

8.1.1 *Serious Adverse Event*

A serious adverse event (SAE) is one that meets one or more of the following criteria:

- Results in death
- Is life-threatening (places the participant at immediate risk of death from the event as it occurred)
- Results in inpatient hospitalization or prolongation of existing hospitalization
- Results in a persistent or significant disability or incapacity
- Results in a congenital anomaly or birth defect
- Based upon appropriate medical judgment, the event may jeopardize the participant's health and may require medical or surgical intervention to prevent one of the other outcomes listed in this definition.

8.1.2 *Unanticipated Problems*

The Office for Human Research Protections (OHRP) considers unanticipated problems involving risks to participants or others to include, in general, any incident, experience, or outcome that meets all of the following criteria:

- unexpected in terms of nature, severity, or frequency given (a) the research procedures that are described in the protocol-related documents, such as the IRB-approved research protocol and informed consent document; and (b) the characteristics of the participant population being studied;
- related or possibly related to participation in the research (possibly related means there is a reasonable possibility that the incident, experience, or outcome may have been caused by the procedures involved in the research); and
- suggests that the research places participants or others at a greater risk of harm (including physical, psychological, economic, or social harm) than was previously known or recognized.

8.2 Specification of Safety Parameters

Safety monitoring for this study will focus on unanticipated problems involving risks to participants, including unanticipated problems that meet the definition of a serious adverse event.

8.3 Reporting Procedures

8.3.1 *Unanticipated Problem Reporting*

Per National Dental PBRN procedures, unanticipated incidents and events will be reported to the PI. After the PI is made aware of the incident/event, the following procedures will be followed.

Incidents or events that meet the OHRP criteria for unanticipated problems require the creation and completion of an unanticipated problem report form. OHRP recommends that investigators include the following information when reporting an adverse event, or any other incident, experience, or outcome as an unanticipated problem to the IRB:

- appropriate identifying information for the research protocol, such as the title, investigator's name, and the IRB project number;
- a detailed description of the adverse event, incident, experience, or outcome;
- an explanation of the basis for determining that the adverse event, incident, experience, or outcome represents an unanticipated problem;
- a description of any changes to the protocol or other corrective actions that have been taken or are proposed in response to the unanticipated problem.

To satisfy the requirement for prompt reporting, unanticipated problems will be reported using the following timeline:

- Unanticipated problems that are serious adverse events will be reported to the IRB as soon as possible or within 5 working days of the investigator becoming aware of the event.
- Any other unanticipated problem will be reported to the IRB within 10 working days of the investigator becoming aware of the problem.
- All unanticipated problems should be reported to appropriate institutional officials (as required by an institution's written reporting procedures), the supporting agency head (or designee), and OHRP within one month of the IRB's receipt of the report of the problem from the investigator.

All unanticipated problems will be reported to NIDCR concurrently with reporting to the IRB. These reports will be made to NIDCR's centralized reporting system via the Clinical Research Operations and Management Support (CROMS) contractor.

- Product Safety Fax Line (US): [name]
- Product Safety Fax Line (International): [contact]
- Product Safety Email: [contact]

9 STUDY OVERSIGHT

The PI will be responsible for study oversight, including monitoring safety, ensuring that the study is conducted according to the protocol and ensuring data integrity. The NCC will provide the PI with current data summaries, and the PI will review the data for safety concerns and data trends at regular intervals, and will promptly submit reportable events to the IRB and NIDCR that arise during the conduct of the study, per the IRB's reporting time-frame requirements. To ensure data integrity, the PI, NCC, and study team will adhere to data quality management processes (please see Section 13).

10 CLINICAL SITE MONITORING

10.1 Site Monitoring

For Network studies, Quality Management procedures and clinical site monitoring (if needed) are conducted to ensure that the study is implemented in accordance with the protocol and other operating procedures, the quality and integrity of study data and data collection methods are maintained, and the safety of human subjects is ensured.

10.2 Site Monitoring Determination

Site monitoring may be needed if there are issues at a practitioner location or office that cannot be addressed via Network quality management processes and office staff re-training. Examples include determining the root cause of an unresolved issue, problematic data found via other quality management processes (e.g., study monitoring reports), and/or problems with informed consent. Efforts will be made to work with the practitioner to resolve site issues before considering a remote or in-person site monitoring visit. In addition, for-cause visits at practices or Central or Node Administrative Sites can be mandated by the NIDCR Office of Clinical Trials Operations & Management (OCTOM), its designees, or can be requested by the NCC, regional staff, or practices.

10.3 Scope of Monitoring Activities

Should there be a need, for-cause study monitoring will be detailed in a Clinical Monitoring Plan developed by NIDCR's CROMS contractor in conjunction with NIDCR. NIDCR will determine where a monitoring visit may occur (e.g., practice, regional Node, central administrative site), whether a for-cause monitoring visit will be performed through the CROMS contractor, and the extent to which network personnel may provide support towards obtaining the documentation needed for the monitoring visit. OCTOM will also determine whether a monitoring visit will be conducted in-person or remotely. The intent of the visit is to address any problems or issues encountered that may require additional training, remediation, or in-person assistance. The scope of the visit will be determined by the issue(s) identified.

11 STATISTICAL CONSIDERATIONS

11.1 Study Hypotheses

Hypothesis 1: The 3-year cumulative incidence of at least one biologic complication of dental implants is 50% amongst patients receiving dental implant therapy in a private practice setting.

Hypothesis 2: The 3-year cumulative incidence of at least one prosthetic complication of dental implants is 50% amongst patients receiving dental implant therapy in a private practice setting.

Hypothesis 3: Incidence of biological complications varies by prosthesis type: screw retained prosthesis have a lower incidence of biologic complications

Hypothesis 4: Incidence of prosthetic complications varies by prosthesis type: cemented restorations have a lower incidence of prosthetic complications

11.2 Sample Size Considerations

The primary objective of the study is descriptive (i.e., to determine the incidence of various outcomes among patients receiving dental implants). As such, a power analysis is based on the precision with which we can estimate the proportion of the occurrence of the primary outcomes (Peri-implant mucositis, Peri-implantitis) among all eligible patients. The study plan is to recruit approximately N=1550 patients with a total of approximately 2000 dental implants. In a published meta-analysis, the prevalence of Peri-implant mucositis was estimated to be 50% and the prevalence of Peri-implantitis was estimated to be around 20% within the three year follow-up period^{7,9,32}. To a good approximation, if W is the width of the 95% confidence interval (i.e., the confidence interval is of the form $P \pm W/2$) for an estimated proportion P based on N observations, then the number of participants (N) needed to achieve that width is given by

$$N = 16 * P * (1 - P) / (W^2) ,$$

where P and W are expressed on a fractional basis. For a given value of W, the formula above is symmetric about P=0.5 and W is largest for P=0.5. Table 1 and figure 1 show the different precision (i.e., width) of our estimated 95% confidence intervals as the underlying cumulative incidence of complications varies.

Table 1.

		width of the 95% confidence interval (W)	
expected 3-year prevalence and cumulative incidence of participant-level complications	N = 1400	N=800	N=500

20%	0.043	0.057	0.072
25%	0.046	0.061	0.078
30%	0.049	0.065	0.082
35%	0.051	0.067	0.086
40%	0.052	0.069	0.088
45%	0.053	0.070	0.089
50%	0.053	0.071	0.090

The secondary objective is to assess association between risk factors and the biologic and prosthetic outcomes. The primary outcomes are Peri-implant mucositis and Peri-implantitis. Based on the assumptions of equal category size, a cluster size of 1.4, and a prevalence of 50% for Peri-implant mucositis and 20% for Peri-implantitis in the reference group, table 2 presents the outcome prevalence values we can detect with varying degree of intracluster correlation coefficient (ICC).

Table 2.

Detectable outcome prevalence values		
ICC	Reference group outcome prevalence values = 50%	Reference group outcome prevalence values = 20%
0.1	56.43%	25.40%
0.2	56.55%	25.50%
0.3	56.67%	25.61%
0.4	56.78%	25.71%
0.5	56.90%	25.81%

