4 STUDY DESIGN

- This is a prospective, observational 3-year cohort study of patients who undergo dental implant restoration by practitioners of the National Dental PBRN. Practitioners who restore dental implants will recruit and enroll their patients in this cohort study during the prosthetic phase of implant therapy.
- Approximately 200 practitioners from all 6 Network Nodes (approximately 35 practitioners per Node) will participate in the study, with each practitioner contributing approximately 10 patients and a maximum of approximately 50 implants.
- The patient population will comprise patients who plan to receive dental implant restorations provided by practitioners of the National Dental PBRN. Approximately 1550 patients will be enrolled until approximately 2000 implants are available for longitudinal observation. Implants will be clustered within patients and within approximately 200 dental practitioners across network practices. Each enrolled patient can contribute more than one implant if multiple implants will be restored at the baseline visit.
- Practitioner and practice characteristics from the National Dental PBRN Enrollment Questionnaire will be combined with data collected for this observational study.
- The prospective, observational study design will allow an opportunity to inform our knowledge of parameters for implant success and risk factors for biologic and prosthetic complications associated with implant therapy. The study will describe the implant restorative therapy provided by the practitioners, the incidence and prevalence of biologic and prosthetic complications, and will correlate patient-level factors, prosthetic- and implant-level characteristics with the risk for implant complications and the therapies provided for dental implant complications.

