5.4.2 Patient Recruitment and Retention

The target sample size for this observational study is approximately 1550 patients and approximately 2000 implants, clustered within approximately 200 dental practitioners across all 6 Network Nodes. Patients planned for implant prosthetic placement will be recruited by practitioners and/or their office staff over a recruitment period of approximately 12 months. Practitioners will be asked to use a consecutive enrollment strategy. Each practitioner will establish a regular recruitment period (days and/or times) each week that fits the practice and is sufficient to meet enrollment targets. A screening criteria log will be used to record potential patient refusal/non-enrollment and, where allowed, reasons for non-enrollment, during established recruiting periods. Practitioners' recruitment schedules may be adjusted at any time with the consultation of the NC. Each practitioner will be asked to contribute approximately 10 patients, with a maximum of approximately 50 implants per practitioner.

Office staff may provide an information sheet and instruct the patient to discuss the study with the practitioner. All patients presenting at participating Network practices may be considered for eligibility after screening by the practitioners and/or trained office staff. The practitioner or other appropriately trained staff members will ask the patient if the patient wants to enroll in the study, provide the patient with an information sheet if the patient does not already have one, and will obtain the verbal authorization to put their information into the HUB.

Patient retention is important to this study. Patients will be remunerated \$25 for the baseline data collection visit and \$25 for each of the three annual follow-up visits. Payments will be processed for each completed part of the study.

Study practitioners will be contacted prior to each follow-up data collection interval. The NCC will create reports with practitioner and patient windows that can be accessed by NCs. Node personnel will remind practitioners to follow-up with non-responders prior to the close of each data collection window and may use mail, email, telephone and/or text messages to encourage the scheduling of the follow-up visits.

Opportunities for engagement of the practitioners with the study team may be created throughout the study in the form of webinar based continuing education sessions on topics of interest to the practitioners.

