11.3 Final Analysis Plan

Data quality. Before we carry out any statistical analyses, we will audit the data for quality and completeness. We will examine variable distributions for outliers and ensure that the data distributions meet the assumptions of the planned analysis. We will present the baseline characteristics as means and standard deviations for continuous variables and as counts and percentages for categorical variables. All inferential tests will be carried out at a two-tailed alpha level of .05.

Missing data. We will examine rates and patterns of missingness. If the missing at random (MAR) assumption is met, a common occurrence, we will perform multiple imputation (MI) analysis to impute missing outcome values when the rate of missingness is between 10% and 50%. Results will be reported for both the imputed data sets and a data set including only those who had complete data (“completers only”) for comparison purposes.

Primary Objectives. To quantify the incidence and prevalence of biologic complications and prosthetic complications among patients receiving dental implant therapy in a private practice setting.

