For biologic complications, three binary outcomes will be examined: Peri-implant mucositis, Peri-implantitis and implant failure. For prosthetic complications, six binary outcomes will be examined including loosening of screws, screw fracture, structural fracture, resin or porcelain fractures, loss of retention, and abutment/ implant misfit. For the primary analysis, all outcomes will be defined at the person level and will be binary (Y/N) regardless of the number of complications experienced per participant. The 3-year cumulative incidence will be calculated as a ratio, where the numerator will be the total number of persons with one or more new (not existing at baseline) complications by the end of the follow-up period, and the denominator will be the total number of persons at risk for that complication at baseline. The prevalence will be calculated using the total number of persons with a complication (both new and existing) divided by the total number of persons at risk during each time interval (baseline, year 1, 2, and 3). In addition, the incidence and prevalence will be computed separately by age group, DM, smoking status, medication use, Osteoporosis, Radiation therapy, Periodontitis diagnosis, and Gingivitis diagnosis. We will calculate incidence and prevalence for all complications except implant failure (incidence only). If data permits, we'll also examine the number and rates of repeated prosthetic complications and the disease progression in biologic complications (mm bone loss over time) for exploratory analysis.

Secondary Objectives. To examine risk factors for biologic and prosthetic complications among patients receiving dental implant therapy in a private practice setting.

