The unit of analysis for the secondary objectives are at the implant level for the biologic complications and the prosthesis level for the prosthetic complications. All the outcomes are binary outcomes (Y/N), and for primary analysis only the first occurrence will be considered. Multiple implants/ prostheses are clustered within the same patient, and multiple patients clustered within practitioners. To account for these correlations, General Estimating Equations (GEE) will be used to identify practitioner, patient and implant variables that are associated with the complications. A binomial model with a logit link function will be used for these binary outcomes. Separate analyses will be conducted for each complication. The variables in table 3 will be considered as potential risk factors.

Secondary analysis will evaluate the association between patient/implant/prosthetic risk factors and the rates of repeated prosthetic complications and the disease progression in biologic complications. For the rates of prosthetic complications, the outcome will be the number (count) of prosthetic complications during the 3-year follow-up period. The unit of analysis will be at the person level, and Poisson models will be used to identify practitioner, patient and prosthesis risk factors that are associated with a higher rate of prosthetic complications. For disease progression in biologic complications, the outcome will be mm bone loss (continuous) over time. Mixed effects model will be used to

account for the longitudinal nature of the data and to identify the practitioner, patient and implant risk factors that are associated with a higher amount of bone loss.

Table 3.

Practitioner level factors	
Number of implants restored per month	biologic and prosthetic complications
Years in practice	biologic and prosthetic complications
Post graduate education	biologic and prosthetic complications
Specialty training	biologic and prosthetic complications
Patient level risk factor	outcome
Age at baseline	biologic and prosthetic complications
Diabetes Mellitus	biologic complications
Smoking status	biologic complications
Medication use SSRI Bone sparing drugs Corticosteroid use	biologic complications
Osteoporosis	biologic complications
Radiation therapy	biologic complications
Periodontitis diagnosis	biologic complications
Gingivitis diagnosis	biologic complications
Parafunctional habits	prosthetic complications
Implant/ Prosthesis level risk factor	

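### Table 1 states 95% interval widths with no allowance for patients being clustered within about 200 practitioners, so the stated precision is too narrow unless that clustering is negligible

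*Protocol*

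**What the plan says.** Section 11.2 calls the primary objective descriptive and bases the sample size on precision. It gives N = 16·P·(1 − P)/W², with W the full width of the 95% interval, and adds: "Table 1 and figure 1 show the different precision (i.e., width) of our estimated 95% confidence intervals". The rows of Table 1 are labelled "expected 3-year prevalence and cumulative incidence of participant-level complications", and the columns are N = 1400, 800 and 500. Recruitment is described thus: "The study plan is to recruit approximately N=1550 patients with a total of approximately 2000 dental implants". Table 1 has no ICC and no design effect. Table 2, for the secondary objective, varies an ICC from 0.1 to 0.5 with a cluster size of 1.4.

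The design is clustered by the protocol's own account. Section 4: "Implants will be clustered within patients and within approximately 200 dental practitioners across network practices". Section 5.4.2 asks each practitioner for about 10 patients, "with a maximum of approximately 50 implants per practitioner". For the secondary objectives, Section 11.3 acknowledges "multiple patients clustered within practitioners" and uses GEE to account for it. For the primary objectives the same section says only "The 3-year cumulative incidence will be calculated as a ratio", at person level, and names no interval or variance method.

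**The concern.** The formula behind Table 1 is valid only if patients' outcomes are independent. Reducing each patient to a single yes/no outcome removes the correlation between implants in the same mouth. It does not remove the correlation between patients of the same practitioner.

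Such correlation is plausible here. Under Sections 3.1 and 7.1 the practitioner records bleeding, exudate and prosthetic complications in his or her own patients, and also provides the prosthesis and the maintenance care. Bone loss, which defines peri-implantitis, is measured centrally by calibrated examiners (Sections 3.1 and 7.3). For that outcome, any clustering would come from shared case mix and care and not from the assessor.

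What is at stake is the one quantity on which the primary sample size is justified. If practitioner clustering is more than trivial, the design will deliver wider intervals than the protocol states.

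**Working it through.** **Inputs.** From the protocol: N = 1400 (largest column of Table 1); P = 20% and 50%; about 200 practitioners; stated widths 0.043 (P = 20%) and 0.053 (P = 50%). Assumed, because the protocol does not give them: a practitioner ICC of 0.02 to 0.20 and, in one variant, a coefficient of variation (CV) of cluster size of 0.8.

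**Step 1: reproduce Table 1.** W = 4·√(P(1 − P)/N).

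- P = 50%: 4·√(0.25/1400) = 0.0535 (stated 0.053).
- P = 20%: 4·√(0.16/1400) = 0.0428 (stated 0.043).

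All 21 cells agree to within 0.001, so the table carries a design effect of 1.

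**Step 2: what Table 2 covers.** Taking 1400 × 1.4 = 1960 implants in two equal groups, a design effect of 1 + 0.4·ICC and 80% power (assumed), the detectable values are 56.44% and 25.40% at ICC 0.1 (stated 56.43% and 25.40%) and 56.91% and 25.82% at ICC 0.5 (stated 56.90% and 25.81%). Table 2 therefore adjusts for implants within patients only. The practitioner level is in neither table.

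**Step 3: add the practitioner level.** With m = 1400/200 = 7, DE = 1 + (m − 1)·ICC = 1 + 6·ICC, and W is multiplied by √DE.

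| Practitioner ICC | DE | √DE | Effective N = 1400/DE | W at 50% | W at 20% |
|---|---|---|---|---|---|
| 0 (Table 1) | 1.00 | 1.00 | 1400 | 0.053 | 0.043 |
| 0.02 | 1.12 | 1.06 | 1250 | 0.057 | 0.045 |
| 0.05 | 1.30 | 1.14 | 1077 | 0.061 | 0.049 |
| 0.10 | 1.60 | 1.26 | 875 | 0.068 | 0.054 |
| 0.20 | 2.20 | 1.48 | 636 | 0.079 | 0.063 |

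**Step 4: slack in the formula.** Using 4 in place of 2 × 1.96 builds in a design effect of (2/1.96)² = 1.041, which corresponds to an ICC of 0.041/6 ≈ 0.007. Above that value the stated widths are too narrow.

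**Step 5: cluster size.** Ten patients from each of 200 practitioners would be 2000, not 1550, so m itself is not settled (1550/200 = 7.75). With m = 10 and N kept at 1400, W at 50% is 0.064 at ICC 0.05 (DE 1.45) and 0.074 at ICC 0.10 (DE 1.90).

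For unequal clusters, DE = 1 + [(1 + CV²)·m − 1]·ICC. With CV 0.8, m = 7 and ICC 0.10, DE = 1 + (1.64 × 7 − 1) × 0.10 = 2.05, and W at 50% is about 0.076.

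**Step 6: conditional coverage.** If the final intervals were computed with the Table 1 formula, their true coverage would be 2Φ(1.96/√DE) − 1, which is about 91% at ICC 0.05 and 88% at ICC 0.10 (m = 7).

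**The case against.** The best defence is that Table 1 is correctly calculated, that the practitioner ICC is unknown, and that the N = 800 and N = 500 columns already show widths up to 0.071 and 0.090 at P = 50%. Every inflated width above lies within that printed range. Even at ICC 0.20 the interval is about ±4 percentage points, which is adequate for a descriptive registry.

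Much of this stands. The arithmetic is right; what is missing is an assumption. The size of the effect depends on an ICC that the protocol does not supply, and at 0.02 it is small. Feasibility is not in doubt. The extra columns do not close the gap, however. The formula defines N as a number of participants, nothing presents 800 or 500 as effective sample sizes, and those columns are uninflated too. An unknown ICC is a reason to show a range, as Table 2 does for implants within patients.

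A reader might infer more than the protocol supports:

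- **That the primary analysis treats patients as independent, so that its intervals will under-cover.** Section 11.3 defines the point estimate as a ratio and is silent on its variance. A statistical analysis plan could specify a clustered interval. The coverage figures in Step 6 apply only if the Table 1 formula is used for the analysis.
- **That tests of Hypotheses 1 and 2 will be anti-conservative.** Section 11.3 says "All inferential tests will be carried out at a two-tailed alpha level of .05", but no test of either 50% value is specified.
- **That practitioners assess every primary outcome.** Bone loss is read centrally.
- **That the cap shows a fivefold spread in cluster size.** The cap of about 50 counts implants, while the 10 counts patients, so the two cannot be compared directly. Unequal clusters are likely, but the CV of 0.8 is an assumption.

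**Conclusion.** The point holds for Table 1. Its widths assume no correlation among patients of the same practitioner, while the protocol elsewhere states that clustering and adjusts for it in the secondary analysis. Against Table 1's unrounded values, the widths at m = 7 are about 6% larger at ICC 0.02, 14% at 0.05, 26% at 0.10 and 48% at 0.20. The error disappears only if the practitioner ICC is about 0.007 or less. These figures rest on an assumed ICC range, on about 200 practitioners of equal size with 1400 patients in all, and, for the unequal-cluster variant, on an assumed CV.

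Severity is moderate. The stated precision is the sole basis for the primary sample size and should be right, but no recruitment target, outcome or point estimate changes. The documents do not support a claim that the sample is too small or that the primary analysis is already committed to invalid intervals.

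**What to change.** 1. In Section 11.2, restate Table 1 with DE = 1 + [(1 + CV²)·m − 1]·ICC, over a stated practitioner ICC range (for example 0.02 to 0.20) and a stated m and CV. Give the number of practitioners behind each N column, because m depends on it, and reconcile the 10 patients requested per practitioner with 1550/200 = 7.75.
2. In Section 11.3, under the primary objectives, add a sentence that confidence intervals for the person-level incidence and prevalence use practitioner-clustered variance. An intercept-only GEE with robust standard errors, Taylor linearisation or a bootstrap of practitioners would each do, and would match the treatment already given to the secondary objectives.

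The cost is protocol wording and a software option at analysis. No extra patients or data are needed. The stated widths become somewhat less favourable.
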